2. Usability and reminder feedback assessed through questionnaires
3. Participant self-report of adherence
4. Use of non-prescribed opioids

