2. INTRODUCTION

2.1 STUDY RATIONALE

The United States is in the midst of an opioid epidemic. According to the Substance Abuse and Mental Health Services Administration (SAMHSA) 2016 estimates, 11.5 million people misuse their prescription opioids, 948,000 use heroin, and 2.1 million people meet diagnostic criteria for opioid use disorder (OUD). A documented 42,249 Americans died of opioid overdose in 2016, which is an average of 116 preventable deaths per day ¹. Opioid Agonist Therapy (OAT), such as buprenorphine/naloxone (BUP/NAL), can reduce opioid overdose deaths by at least 70%, decrease opioid misuse, and improve quality of life. Because of its proven efficacy, the National Institute on Drug Abuse (NIDA), the Substance Abuse and Mental Health Services Administration (SAMHSA), the American Society of Addiction Medicine (ASAM), and the American Academy of Addiction Psychiatry (AAAP) endorse the use of medication-assisted therapy in the treatment of OUD.

Poor medication adherence is one of the main barriers to long term efficacy of opioid agonist therapy (OAT). A year-long outpatient study of OAT in 225 treatment-seeking patients with opioid use disorder (OUD)² showed that treatment retention fell to under 50% by 12 weeks and only 25% of patients remained at one year. Novel depot formulations of efficacious drugs can improve adherence. However, in Ling's study, depot opioid agonists provided only a modest increase in adherence (13.8% compared to oral buprenorphine/naloxone BUP/NAL) despite the significant (565%) price increase compared to the generic drug.

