To improve performance, we plan to substantially increase adherence to inexpensive oral BUP/NAL with Pillsy, a smart technology platform developed over the past three years using principles of behavioral science, modern design, and highly scalable wireless and mobile technologies. Pillsy acts like a digital medication coach, providing education and reminders using a mobile app, text messages, and automated phone calls. The platform is built around a Bluetooth-based smart pill bottle cap that automatically tracks doses, timing and sends intelligent reminders to create a unique feedback loop, which allows us to constantly optimize our incentive/reminder messages to meet user needs and increase adherence. Since its recent launch, the company has already over 1,000 clients. Pillsy can substantially increase adherence to OAT and decrease opioid-related morbidity and mortality. Since Pillsy only nominally increases the cost of oral BUP/NAL treatment and providers can bill for monitoring time (CPT code 99091), it is an attractive solution to patients, providers, and payers. However, there are few if any studies available that have systematically investigated this technology's impact on medication adherence in this population.

We will conduct a Phase I study involving 30 subjects selected randomly among patients prescribed (BUP/NAL) for opioid misuse, to better understand their willingness to use Pillsy and identify areas of resistance.

3. OBJECTIVES AND ENDPOINTS.

- 1- Compare Pillsy delivered BUP/NAL adherence to conventional BUP/NAL therapy.
- 2- Evaluate non-prescribed opioid use and therapy retention between groups.
- 3- Understand participants' willingness to use Pillsy and identify areas of resistance.

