4. STUDY POPULATION

Recruitment

Goal: Enroll 30 eligible adults: 15 control group services as usual (SAU); 15 Pillsy group (PLY).

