Study participants will return to office as frequently as the prescriber sees fit in the course of addiction treatment. At 6 weeks +/- 2 days, the RC will count BUP/NAL tablets/sublingual films and compare to the prescribed number of pills for that period. Participants will complete questionnaires.

Week 12 Assessment

Study participants will return to office as frequently as the prescriber sees fit in the course of addiction treatment. At 12 weeks +/- 3 days, or RC will count BUP/NAL tablets/sublingual films

and compare to the prescribed number of pills for that period. Participants will complete questionnaires.

Ongoing Assessments

Pillsy will continuously collect data on pill bottle openings, missed doses, text messages sent, automated phone calls made, etc. If there is a loss of contact, or the participant stops their engagement with the study, the RC will attempt to contact the participant (up to two (2) attempts) with an exit interview, by phone. If no answer, no message will be left. The coordinator will attempt to call again 2-3 business days later for a final attempt to describe reasons for withdrawal from the study.

Table 1. Schedule and Types of Assessments Performed: MAP4BUP Phase I.

	Screening/Baseline	Week 1	Week 6	Week 12
Informed consent	X			
Verify inclusion/exclusion criteria are met	X			
AUDIT	X			
Demographics	X			
Fagerström	X			
Addiction Severity Index – Lite	X			
Timeline Follow-Back of medication use and drug and alcohol use	X	X	X	X
DSM-5 OUD Checklist*	X			
Pill/film count and self-report of prescriptions	X	X	X	X
Barratt Impulsiveness Scale (BIS) 8	X	X	X	X
Opioid Craving Scale	X	X	X	X
Healthy Days Core Module (CDC HRQOL-4)	X	X	X	X
Sleep Related Impairment	X	X	X	X
Sleep Disturbance	X	X	X	X
Pain Intensity	X	X	X	X
Pain Interference	X	X	X	X
Standard counseling, prescribing, dose changes**	As needed, determined by prescribing provider and medical team.			
Pillsy System Usability Questionnaire		X		X
Adverse event monitoring	X	X	X	X
Reason for quitting	Administered once, triggered by predefined non-adherence to the treatment.			

*Diagnostic and Statistical Manual of Mental Disorders, Fifth Edition (DSM-5) Opioid Use Disorder (OUD) research checklist

**To be guided by the discretion and standard practices of the prescriber.

Laboratory Assessment

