The risk to patients from the digital intervention is negligible. The potential benefit of the intervention is improved adherence to opioid agonist/antagonist therapy specifically and medication-assisted therapy in general. This benefit may occur in the patients participating in the trial, and the data collected may extent to future users of the technology.

Medication-assisted therapy is our best hope for combatting the opioid crisis in the near term. Adherence to opioid agonist/antagonist therapy is critical. Pillsy is a technology that can improve adherence to opioid agonist/antagonist therapy and thereby could help curb the current opioid crisis. Since Pillsy is a digital intervention, no physical adverse events are anticipated. However, participants will be undergoing medication-assisted therapy during their clinical care. Patients will be monitored by their respective provider for drug-related adverse events as they would during clinical care. If a provider decides to stop BUP/NAL for any reason (including, but not limited to, a treatment-related adverse event), the participant will also be discontinued from the Pillsy intervention. RCs will attempt to gather subjective feedback about the Pillsy intervention from discontinued participants.

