6. STATISTICAL CONSIDERATIONS

6.1 Sample Size

For this Phase I study we are planning to randomize 15% of the targeted N (200) of a full-scale Phase II study, resulting in a total of 30 subjects, 15 per arm. More than anything, this is designed as a “proof-of-concept” study to demonstrate that Pillsy can produce some amount of adherence improvement and is both feasible and useful to patients so we can plan a larger version of this study in Phase II.

Sample size calculations – Our choice of sample size for the Phase II trial (n=200) was based on power calculations for detecting a 20% increase in our primary outcome of increasing adherence to BUP/NAL while also considering treatment retention assessed by office visits and assuming a 25% attrition rate in our cohort. This translates to an OR of 2.4, which we would have 99% power to find based on 3 longitudinal assessments and assuming we are examining the between effect only. Using a more conservative estimate of a 10% change, we would still have 90% power to detect this effect (OR of 1.6).

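### The Pillsy usability form skips week 6 and is not specified for people who leave, so every scheduled score after about day 7 comes from participants still present at week 12

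*Combined protocol and SAP*

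**What the plan says.** Objective 3 (Section 3) is to "Understand participants' willingness to use Pillsy and identify areas of resistance". Secondary endpoint 2 (Section 1.1) is "Usability and reminder feedback assessed through questionnaires".

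The scheduled instrument is the "Pillsy System Usability Questionnaire" in Table 1 (Section 5), marked at week 1 and week 12. The week 1 visit has a window of one day either side, so the first score falls on days 6 to 8. Week 6 is a full study visit. Table 1 gives the pill or film count, the Timeline Follow-Back, seven other questionnaires (impulsiveness, craving, healthy days, two on sleep, two on pain) and adverse event monitoring there, but no usability form.

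Three routes reach people who leave:

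- **Exit interview** (Section 5, Ongoing Assessments). It is done by phone with at most two attempts and no message left. The second is described as a "final attempt to describe reasons for withdrawal from the study".
- **Reason for quitting row** (Table 1). It is given once, when a predefined level of treatment non-adherence is reached. The text does not define that level.
- **Discontinuation contact** (Section 5.1.3): "RCs will attempt to gather subjective feedback about the Pillsy intervention from discontinued participants". No instrument or timing is named.

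Real-time surveys (Section 1.1, under engagement) and continuous cap and reminder data (Section 5) add information between visits.

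Section 6.2 plans repeated-measures methods for the secondary outcomes. Section 6.4 favours maximum likelihood or multiple imputation and keeps dropouts in the analysis up to withdrawal.

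**The concern.** The two scheduled readings are 11 weeks apart. The first reflects about a week of use. The second exists only for those who attend at week 12. Someone who tires of the reminders, automated calls or helper messages in between is direct evidence on objective 3, yet the schedule records that person's view only as a first-week impression.

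If such people are more likely to leave, the week 12 score overstates how acceptable Pillsy is, and the features that put people off are less visible. Section 6.1 presents Phase I as a proof of concept, meant to show that Pillsy is feasible and useful to patients and to support planning of Phase II. Usability evidence is therefore one of the study's main products.

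**Working it through.** **Inputs**

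- Arm size. Section 6.1 takes 15% of the Phase II target of 200, "resulting in a total of 30 subjects, 15 per arm". Check: 0.15 × 200 = 30, or 15 per arm. The figure reproduces.
- Attrition of 25%. This is stated in Section 6.1 within the Phase II sample size calculation.
- Retention under 50% at 12 weeks. Section 2.1 reports a cited study of 225 patients in which "treatment retention fell to under 50% by 12 weeks and only 25% of patients remained at one year". This is treatment retention, not attrition from a study like this one.
- The count is made in the Pillsy arm, because only that arm receives the app and reminders. Table 1 does not name an arm for the form.

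**Step 1. Who has a scheduled score after week 1?** Completers = 15 × retention.

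| Assumed 12-week retention | With a week 12 score | Without one |
|---|---|---|
| 75% | 15 × 0.75 = 11.25 | 3.75, about 4 |
| 50% | 15 × 0.50 = 7.5 | 7.5, about 8 |

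The cited figure is below 50%, so 8 is the lower end for that source. Chance variation in an arm of 15 is wide (binomial). At 75% retention, the probability of 10 to 13 completers is 0.920 − 0.148 = 0.77. At 50%, the probability of 6 to 9 completers is 0.849 − 0.151 = 0.70.

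**Step 2. What would a week 6 form add?** Assume a constant dropout rate, which the protocol does not state. Retention at week 6 is then the square root of retention at week 12.

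- 75%: √0.75 = 0.866, and 15 × 0.866 = 13.0 are present at week 6. Later leavers captured: 13.0 − 11.25 = 1.7 of 3.75.
- 50%: √0.50 = 0.707, and 15 × 0.707 = 10.6 are present. Later leavers captured: 10.6 − 7.5 = 3.1 of 7.5.

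A week 6 form reaches about 2 to 3 people who later leave, which is fewer than half of all leavers. It would reach fewer still if dropout is concentrated early. The exit and discontinuation contacts have to supply the rest.

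**Step 3. How much might the exit calls already supply?** The protocol gives no contact rate. Let q be the assumed success per call, so two calls reach 1 − (1 − q)² of leavers. Leavers' share of everyone giving feedback after week 1 is leavers reached ÷ (leavers reached + completers).

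| q (assumed) | Reached | Share, 25% attrition | Share, 50% attrition |
|---|---|---|---|
| 10% | 19% | 0.71 / 11.96 = 6% | 1.42 / 8.92 = 16% |
| 20% | 36% | 11% | 26% |
| 30% | 51% | 14% | 34% |
| 50% | 75% | 2.81 / 14.06 = 20% | 5.62 / 13.12 = 43% |

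Leavers may therefore contribute a real share of the feedback. What they contribute has no specified usability items, so it cannot be set beside the week 1 and week 12 scores.

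**The case against.** The strongest reply is that the plan does not ignore leavers. It has an exit interview, a quitting form and a promise to seek Pillsy feedback from discontinued participants, besides real-time surveys and cap data up to the point of leaving. Objective 3 is not tied to the usability form, and open feedback is a reasonable way to learn about resistance. Leavers' week 1 scores also stay in the analysis under Section 6.4.

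Most of this stands, and it rules out several stronger readings:

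- A reader might infer that objective 3 is answered almost only by those who stayed. Attrition shows how many leave, not how many are silent, and Step 3 shows that leavers' share could be substantial.
- A reader might infer that the exit interview contains no usability items. Its items are not listed. Only its purpose is given, so the supportable statement is that none are specified.
- A reader might infer a large, known upward bias. The documents do not say how leavers rate Pillsy. Some will leave for unrelated reasons: under Section 5.1.3, Pillsy ends whenever a provider stops the medication, whatever the reason.
- Neither loss figure is a Phase I estimate.

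The reply does not supply a comparable score. The quitting form is triggered by treatment non-adherence, so it may miss someone who stays on medication but abandons Pillsy. The real-time surveys are listed under engagement. Cap data show what happened, not why. For people lost after week 1, likelihood or imputation methods have only a first-week score on this instrument to work from.

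**Conclusion.** The point holds for the scheduled questionnaire: after about day 7, every scheduled usability score comes from someone present at week 12. If Phase I loss resembles the protocol's only two figures, about 4 to 8 of 15 Pillsy participants would have no comparable later score. Upward bias in secondary endpoint 2 is plausible but unmeasured, and requires leavers to be less satisfied than completers. Objective 3 is weakened but not left unanswered. The primary endpoint is unaffected. This is a cheap improvement rather than a flaw that undermines the study.

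**What to change.** 1. In Table 1, add the usability questionnaire at week 6.
2. Give the same short items at the exit interview and at the discontinuation contact in Section 5.1.3.
3. Report usability by visit, and separately for completers and leavers, with the number responding in each group. Use the repeated-measures and missing-data methods of Sections 6.2 and 6.4. Do not carry the last rating forward: for a leaver who is not reached, that would present the first-week impression as a final view and mix ratings taken after very different lengths of use.

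No new visit or staff is needed. The cost is a few minutes of participant time at week 6 and slightly longer exit calls.

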5.1 Assessment of Safety

Ideal Option has robust Diversion Control and Patient Safety policies in place to ensure that patients are taking their medication as prescribed. Providers are supplied with a variety of clinical tools to uphold patient safety while not disturbing the trust in the patient-provider relationship. Further, Ideal Option has a robust Nurse Care Team which provides support and continuing education to all its providers.

5.1.1 Adverse events (AE)

According to the code of federal regulation title 21 of the Food and Drug Administration (FDA), an Adverse event refers to any untoward medical occurrence associated with the use of a drug in humans, whether considered drug related or not.

All AEs, whether volunteered, elicited, or noted on physical examination, will be recorded throughout the study (i.e., from signing of the ICF until completion).

All AEs will be collected in and recorded in REDCap.

Classification of an Adverse Event

Severity of event

Each AE will be assigned a category by the Investigator as follows:

Mild: An AE that is easily tolerated by the subject, requires minimal or no treatment and does not interfere with the participant's daily activities.

Moderate: An AE that results in a low level of inconvenience or concern by therapeutic measures. Moderate events may cause some interference with functioning. Intervention may be needed.

Severe: An AE that prevents normal everyday activities and may require systemic drug therapy or other treatment. Severe events are usually potentially life-threatening or incapacitating. If there is a change in severity of an AE, it must be recorded as a separate event.

Relationship of Event

The Investigator will make every effort to assess the relationship of the AE, if any, to the study intervention. The Investigator should use knowledge of the subject, the circumstances surrounding the event, and an evaluation of any potential alternative causes to determine

whether an AE is related to the study treatment. Causality should be assessed using the categories presented below:

Related: The AE is known to occur with the study intervention, there is a reasonable possibility that the study intervention caused the AE, or there is a temporal relationship between the study intervention and event. "Reasonable possibility" means that there is evidence to suggest a causal relationship between the study intervention and the AE.

Not Related: There is no reasonable possibility that the administration of the study intervention caused the event. There is no temporal relationship between the study intervention and event onset, or an alternate etiology has been established.

Action Taken

The investigator will describe the action taken in the appropriate section in REDCap, as follows:

- None
- Study procedure or medication stopped
- Study medication temporarily interrupted
- Concomitant medication
- Other, specify

Reporting Adverse Events

All adverse events should be documented in accordance with the procedures outlined below. All AEs occurring during the study must be documented on the relevant CRF pages. The following information should be documented for each AE:

- Description of the symptom event
- Classification of "serious" or "not serious"
- Severity
- Date of first occurrence and date of resolution (if applicable)
- Action taken
- Causal relationship
- Outcome of the event (unknown, recovered, not yet recovered, recovered with sequelae, death)

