If the patient does not take their medicine at the correct time, a light on the smart pill cap begins to flash. If the bottle is not opened within 20 minutes, the Pillsy application sends an SMS text reminder to the patient's phone. If the bottle is not opened within 60 minutes, the patient receives an automated phone call. The patient may also receive brief motivational phrases that can be tailored to patient needs and preferences. Pillsy also includes a "Pillsy Helpers" feature in which the patient can name friends and family members who will also receive a text message notification one hour after a missed dose. Thus, if the patient is struggling, his or her support system can attempt to contact the patient and offer motivation. Importantly, as proposed in the clinical trials detailed in this application, the MAT prescriber can also be a Pillsy Helper.

All data handling will conform to meet HIPAA requirements, including administrative, physical, and technical safeguards. Data will be encrypted in storage and in rest in REDCap with regularly scheduled data deposits from Pillsy into REDCap.

Participants in the service as usual (SAU) arm will receive a prescription for BUP/NAL tablets/sublingual films and any services normally provided by the prescribing office. Participants in the SAU arm will receive an "inactive" Pillsy smart cap that will track openings but will not provide reminders or any other messaging.

Screening Visit

The RC will screen the patient to assess the participant's appropriateness for the study. If the prospective participant meets inclusion/exclusion criteria, the RC will explain the clinical study in detail and informed consent will be obtained. If eligible, the participant will be trained on how to use the Pillsy system (cap and app) if randomized to PLY group. No training will be needed for the SAU. While their cap will be activated to capture open and close times, that is the only data that will be collected on the cap. and randomized to one of the study groups.

Week 1 Assessment

Study participants will return to office as frequently as the prescriber sees fit in the course of addiction treatment. At 1 week +/- 1 day, the RC will count BUP/NAL tablets/sublingual films and compare to the prescribed number of pills for that period. Participants will complete questionnaires.

Week 6 Assessment

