5.1.3 Other Safety Considerations

Data and Safety Monitoring Plan

Patients receiving opioid use disorder treatment will receive care as usual. Half of the participants will also receive the Pillsy intervention. The Pillsy intervention is a smart pill cap, mobile application with text and other messaging capability. We will keep enrollment to the lowest numbers possible that still allow sufficient power to answer research questions.

The risk to patients from the digital intervention is negligible. All data is collected in a HIPAA-compliant manner. Private identifiable information will be encrypted and kept secure.

Study visits will be conducted in a manner to protect participant privacy. The consent process, administration of questionnaires, etc. will occur in a private area. To reduce the risk of unauthorized disclosure of confidential information all personal identifiers will be kept separate from participant files and a study specific research identification number (key) will be assigned to each participant. Data will be collected, entered and accessed by study personnel trained in issues of confidentiality related to human subject protection. The key will be kept separate and not in the same enclave component of the network. Data will be entered into a password-protected database that is encrypted and firewalled. The consent form states that all information provided by the participant will be kept private except in the case that this would immediately put the participant or someone else in danger. In that case the Investigator would release information to keep the participant or another person safe. The consent states that if

Investigator learn about abuse to a child or an elder, that information must be reported to the proper authorities.

As in all research of this nature, there is the possibility of discomfort or embarrassment related to questions dealing with opioid use and social stigma for engaging in these types of behaviors. Participants will be informed that they have the right to refuse to answer any question. If participants find any aspects of their involvement in the research study particularly distressing, they will be encouraged to discontinue participation.

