6.5 Safety Analysis

While we anticipate a very low rate of adverse events, the medical monitor will compare AEs and SAEs between the two arms. We will conduct this analysis to inform the Phase II clinical trial of this intervention.

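### The AE definition is medical and drug-framed, so the AE/SAE comparison in 6.5 is likely to miss non-medical harms of the Pillsy system

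*Combined protocol and SAP*

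**What the plan says.** Section 5.1.1 states that "an Adverse event refers to any untoward medical occurrence associated with the use of a drug in humans", and adds that this applies whether or not the drug is thought to be the cause. Collection runs from consent to completion and takes in events that are reported spontaneously, drawn out by questioning or found on examination. Causality is judged against Pillsy as well: "The Investigator will make every effort to assess the relationship of the AE, if any, to the study intervention".

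The Intervention text in section 5 describes what differs between the arms. Both arms get a cap that tracks openings and both are prescribed BUP/NAL. Only the Pillsy arm gets a flashing cap, SMS reminders, automated calls and the helper feature, under which a participant can "name friends and family members who will also receive a text message notification one hour after a missed dose". The prescriber may also be a helper.

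Section 5.1.3 says that "The risk to patients from the digital intervention is negligible" and that no physical adverse events are expected from a digital intervention. The risks it does discuss are unauthorised disclosure of study data, and embarrassment or stigma from questions about opioid use. If any part of taking part proves particularly distressing to participants, "they will be encouraged to discontinue participation".

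Section 6.5 has the medical monitor compare AEs and SAEs between arms, and gives the purpose: "We will conduct this analysis to inform the Phase II clinical trial of this intervention".

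**The concern.** The definition suits a drug trial, but the drug is not what is randomised. By the plan's own reasoning, harms of Pillsy would be mostly non-physical, and that is the kind a medical definition is least suited to catch. The route most specific to Pillsy, a text to a third party about a missed dose of opioid use disorder treatment, is not listed among the risks in 5.1.3 and has no place in the event record.

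At stake is the single safety output meant for Phase II. A clean AE table could be read as support for the negligible-risk statement when the harms in question had no defined way of entering the table. A participant who left because of helper texts or repeated calls could appear as a withdrawal and not as a harm.

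**Working it through.** No figure in the plan is in dispute, and the plan gives no expected AE rate or safety power, so there is nothing to reproduce. The check sets the sections side by side and then gives an illustration under assumed rates.

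**Which harms can reach 6.5?**

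| Event in a Pillsy participant | Recordable as an AE? | Collected elsewhere? | Feeds 6.5? |
|---|---|---|---|
| Medical or psychiatric event, any cause | Yes (5.1.1) | – | Yes |
| Suicidal ideation | Yes, by a separate instruction in section 8 to use the Adverse Event Log | – | Yes, as a log entry |
| Disclosure of treatment, or conflict, through a helper text | Not stated | Possibly, in an exit interview | No |
| Message or call burden | Not stated | Usability questionnaire, weeks 1 and 12 (Table 1) | No |
| Distress short of a medical event, leading to withdrawal | Not stated; 5.1.3 encourages discontinuation without an instruction to record | Exit interview and reason-for-quitting form (section 5, Table 1); feedback from participants discontinued when BUP/NAL is stopped (5.1.3) | No |

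The causality rating in 5.1.1 does not fill the last three rows, because it applies only once something has qualified as an AE.

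**Illustration of size.** Inputs: n = 15 in the Pillsy arm (section 4); true rate p of non-medical harm per participant, assumed at 5%, 10% or 20%; proportion c of such events that is recorded, assumed at 1, 0.5 or 0. The expected number of participants affected is 15 × 0.10 = 1.5 at 10% and 15 × 0.20 = 3 at 20%. The chance of at least one recorded event is 1 − (1 − p·c)^15.

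| p | c = 1 | c = 0.5 | c = 0 |
|---|---|---|---|
| 5% | 1 − 0.95^15 = 53.7% | 1 − 0.975^15 = 31.6% | 0% |
| 10% | 1 − 0.90^15 = 79.4% | 1 − 0.95^15 = 53.7% | 0% |
| 20% | 1 − 0.80^15 = 96.5% | 1 − 0.90^15 = 79.4% | 0% |

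The last column is the literal reading, under which a strictly non-medical event is not an AE.

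**What 15 per arm can show even with full capture.** With 0 events in 15, the upper 95% limit for the true rate is 1 − 0.05^(1/15) = 18.1% one-sided, or 1 − 0.025^(1/15) = 21.8% two-sided. Fisher's exact test, two-sided, gives p = 0.10 for 4 versus 0 events and p = 0.042 for 5 versus 0. The comparison is descriptive under any definition.

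**The case against.** The best defence is that the definition continues past its drug wording and counts events whether or not they are thought drug-related. Every participant is prescribed BUP/NAL, so any medical occurrence, psychiatric ones included, can qualify. Causality is rated against the study intervention, and a temporal relationship is enough for a rating of related. Suicidal ideation is logged. All of this stands. A reader might infer that the safety comparison cannot find any harm of Pillsy; the documents do not support that. The gap is confined to non-medical events.

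Second, much is already collected. Reminder feedback is a secondary endpoint, exit interviews and a reason-for-quitting form are planned, and participants may refuse any question. Pill or film counts and Timeline Follow-Back of medication use at weeks 1, 6 and 12 mean that extra dosing is not unobserved. Helper disclosure is partly mitigated: participants name their own helpers, 4.1 requires one partner who agrees to take part, and the consent video is also aimed at the partner. This stands too, but none of it is routed to 6.5 and no tabulation of withdrawal reasons by arm is planned.

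Three further inferences are tempting and should not be drawn.

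- That the risks named in 5.1.3 are Pillsy's own. The section ties embarrassment to the research questions and disclosure to study data, and both apply to both arms.
- That a dose removed earlier must produce a false missed-dose alert. Reminders depend on the bottle not being opened, but the text does not say how the app treats an earlier tracked opening.
- That drop-out will rise selectively in the Pillsy arm. No figure supports this, and under 6.4 participants who leave stay in the analyses up to withdrawal.

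**Conclusion.** The point holds in limited form. The AE definition has not been adapted to a digital intervention, and 6.5, the only between-arm harm analysis, is likely to miss disclosure or conflict through helper texts, message and call burden, and non-medical distress that ends in withdrawal. Medical and psychiatric harms are covered.

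The size depends on two quantities that the plan does not give: the true rate of such events and how broadly investigators read the definition. Over assumed rates of 5% to 20%, the chance of seeing at least one event in the Pillsy arm is 54% to 96% with full capture, 32% to 79% with half, and zero on the literal reading. A wider definition would not turn 6.5 into a powered comparison. It would make an absence of events informative, within the limit that 0 of 15 is still compatible with a true rate of about 18% (one-sided) to 22% (two-sided). The change should be made, because 6.5 is intended to inform Phase II and the remedy is small.

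**What to change.** - **5.1.1:** define an AE as any untoward medical, psychological or social occurrence after consent, whether or not related to Pillsy or BUP/NAL.
- **AE checks at weeks 1, 6 and 12 (Table 1):** ask both arms about distress from study contact, unintended disclosure of treatment, and conflict with a helper. Ask about a missed-dose alert after a dose was taken, and an extra dose taken after a prompt, in the Pillsy arm only. The SAU cap sends no messages, so those items give a one-arm count, to be reported descriptively.
- **5.1.3:** state that distress is recorded as an event. The wording that encourages distressed participants to discontinue must be reconciled with that aim; no replacement discontinuation rule is proposed here.
- **6.5:** tabulate these events and the withdrawal reasons already collected, by arm, and state that the comparison is descriptive at 15 per arm.

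The cost is a revised definition, about five short questions at visits already scheduled, and one further table. The reported AE count will be higher, and the report should say that this reflects the wider definition.
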